7.8 Treatment duration

This is a single infusion treatment.

7.9 Post treatment follow-up

Participants will be followed-up for 24 months post-treatment.

7.10 Discontinuation/Withdrawal of Participants from Trial Treatment

Each participant has the right to withdraw from the trial at any time. In addition, the Investigator may discontinue a participant from the trial at any time if the Investigator considers it necessary for any reason.

The participants and the parents/guardians of the participants who wish to withdraw from the study will be asked to confirm whether they are still willing to provide data collected as per routine clinical practice at visits. Their follow-up clinical care will be as per routine practice.

If the participant is withdrawn due to an adverse event, the Investigator will arrange for follow-up visits or telephone calls until the adverse event has resolved or stabilised.

If there is a significant reaction to the infusion of cells the infusion will be stopped and the patient will be withdrawn from the study.

If a patient has significant rejection (ISHLT grade III or above), then they will be treated in conjunction with the clinical team's usual practice. [38] This will likely include steroid medicines and potentially other agents as per GOSH policy. They will remain under careful follow up.

In the event that the participant withdraws from the trial, the appropriate withdrawal page in the eCRF should be completed. On the withdrawal page, the Investigator should record the date of the withdrawal, the person who initiated withdrawal and the reason for withdrawal. If a participant is withdrawn from the trial, data already collected for that participant prior to withdrawal will still be analysed and this will be made clear in the PIS and ICF.

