8.12 Participant Withdrawal Criteria

Participants have the right to withdraw from the study at any time for any reason. The investigator also has the right to withdraw patients from the study in the event of inter-current illness, AEs, SAE's, SUSAR's, protocol violations, cure, administrative reasons or any other reasons deemed appropriate. It is understood by all concerned that an excessive rate of withdrawals can render the study un-interpretable; therefore, unnecessary withdrawal of patients should be avoided. Should a patient decide to withdraw from the study, all efforts will be made to report the reason for withdrawal as thoroughly as possible.

As the IMP in this trial is an advanced therapy with a single infusion, participants who wish to withdraw from trial after IMP has been administered, will be asked to confirm whether they are still willing to attend the safety follow up visits as per protocol for the duration of the trial. If participants are not willing to do this, consent will be sought for the trial team to access routine data collected from hospital/GP visits for the duration of the safety follow up period.

In situations where a patient has to be withdrawn or decides to withdraw from the study, an additional patient may be recruited and dosed if:

- They withdraw prior to the TR006 infusion.
- They withdraw during their 4-week follow-up period, and have not yet experienced a DLT.

If a patient withdraws from the trial a withdrawal form in the study database will be completed.

The DMC will review all patients, including any withdrawn patients, to determine if a primary outcome has occurred (DLT, no DLT or DLT not determined in the active period).

In the following situations, the withdrawn patient will have contributed to the primary outcome and no additional patient will be recruited:

- If they withdrew after they completed their 4-week follow-up safety period.
- If they experience a DLT during their 4-week follow-up safety period, which may or may not be the reason for withdrawal.

9 Assessment of Safety

Definitions

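### A child withdrawn for an infusion reaction below the DLT threshold may be replaced and drop out of the 3+3 count, with no guaranteed 4-week DLT assessment

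*Protocol*

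**What the plan says.** Section 7.10 sets a mandatory rule for a child with a significant reaction to the cells: "the infusion will be stopped and the patient will be withdrawn from the study". It gives 'significant' no grade and no link to the DLT list in section 5.1. For withdrawals due to an adverse event, it adds that "the Investigator will arrange for follow-up visits or telephone calls until the adverse event has resolved or stabilised".

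Section 8.12 sets the replacement rule. Its scope includes enforced withdrawals: "In situations where a patient has to be withdrawn or decides to withdraw from the study, an additional patient may be recruited and dosed if". The relevant condition is "They withdraw during their 4-week follow-up period, and have not yet experienced a DLT". It also names the withdrawn patients who do contribute to the primary outcome and are not replaced: "If they withdrew after they completed their 4-week follow-up safety period", or "If they experience a DLT during their 4-week follow-up safety period, which may or may not be the reason for withdrawal". As a safeguard, "The DMC will review all patients, including any withdrawn patients, to determine if a primary outcome has occurred", with three possible results: DLT, no DLT, or not determined.

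Section 5.1 counts CRS, fever or rigors, and injection site reactions as DLTs from grade 2, and bronchospasm and hypoxia from grade 3, all within 72 hours. Over 4 weeks it counts infection, haematological complications and other toxicity from grade 3, and moderate or severe rejection. Sections 10.2 and 10.4 make the DLT count the basis of each cohort decision.

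**The concern.** Section 7.10 ends study participation as well as the infusion, and the trigger for doing so is close to the outcome being measured. Section 8.12 does not ask why a patient left. A child whose reaction is real but below the DLT threshold can therefore be withdrawn on Day 0 and replaced by another child. That child then falls outside both groups that section 8.12 says contribute to the primary outcome.

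With cohorts of three, one child decides between escalating and repeating the dose. If the children removed this way carry more risk than those who replace them, the 3+3 rule sees too few DLTs and escalates too readily. This is a paediatric trial of a product that section 9.2 says has not been given to humans before.

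**Working it through.** **1. Can a reaction stop the infusion without being a DLT?** Yes, in at least two ways.
- Isolated grade 2 bronchospasm is below the grade 3 threshold in section 5.1.
- Section 4.2.1 (Type II hypersensitivity) stops the infusion for a 1°C rise that persists after slowing. Fever graded as CRS grade 1 (section 8.10, Table 13) is not a DLT, and fever counts in its own right only from grade 2. Section 4.2.1 does not mention leaving the study, so whether section 7.10 applies to this child is unclear.

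**2. Would a later DLT be seen?** Infection, rejection, haematological and other grade 3 toxicity count up to week 4. The Day 14 and Day 28 visits (section 7.5) are where the examinations and blood tests fall. For a withdrawn child, section 7.10 guarantees follow-up of the adverse event until it resolves or stabilises, which may be well before Day 28.

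**3. What happens to the count?** The DMC may return 'not determined'. Section 8.12 does not say how that result enters the 3/6 tallies, and replacement stays permitted.

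**4. The plan's own figure.** Following the rules in sections 5.1 and 10.2, completed paths use 9 children (high dose from Cohort 2, or from Cohort 3 without expansion) or 12 (high dose from Cohort 3 with 1/3 DLT). This reproduces the stated 9 to 12. Paths that stop early end at 6. The range makes no allowance for replacements.

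**5. Size, as a scenario.** The protocol gives none of these rates; all are assumptions, taken as equal at both doses:
- r = probability of a sub-DLT reaction leading to withdrawal and replacement
- d = DLT probability in the other children
- h = probability that a withdrawn reactor has a DLT by week 4, or an event judged dose-limiting

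DLT rate with all infused children counted: p = (1 − r)d + rh. With reactors replaced: p = d.

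P(0/3) = (1 − p)³.

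P(high dose declared tolerated) = P(0/3 at low) × P(at most 1/6 at high) + P(1/3 then 0/3 at low) × [P(0/3 at high) + P(1/3 then 0/3 at high)].

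For r = 10%, d = 10%, h = 50%: p = 0.9 × 0.10 + 0.1 × 0.50 = 0.14. Then 0.86³ = 63.6%, against 0.90³ = 72.9%.

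| r | d | h | p, all counted | P(0/3), all / replaced | P(high tolerated), all / replaced |
|---|---|---|---|---|---|
| 5% | 10% | 25% | 10.75% | 71.1% / 72.9% | 78.2% / 80.6% |
| 10% | 10% | 50% | 14.0% | 63.6% / 72.9% | 67.3% / 80.6% |
| 10% | 20% | 50% | 23.0% | 45.7% / 51.2% | 38.6% / 47.5% |
| 20% | 10% | 100% | 28.0% | 37.3% / 72.9% | 26.0% / 80.6% |
| 10% | 10% | 10% | 10.0% | 72.9% / 72.9% | 80.6% / 80.6% |
| 10% | 10% | 0% | 9.0% | 75.4% / 72.9% | 83.7% / 80.6% |

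The bias is downward only when h exceeds d. It is zero when they are equal, and it reverses when h is below d.

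**The case against.** A reader might infer that toxic cases in general are removed from the DLT denominator. The text does not support that. Section 8.12 keeps every child with a DLT in the count, whether or not the DLT caused the withdrawal. The DLT list is also broad for acute reactions: grade 2 hypoxia or hypotension within CRS is already a DLT (section 5.1 with Table 13), so hypoxia as part of a CRS-type reaction is not an example of the gap.

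A reader might also model every replaced child as a true DLT. At a true rate of 30% with half replaced, the effective rate would be 0.15/0.85 = 17.6%, and P(0/3) would rise from 34% to 56%. The arithmetic is right, but it describes children who meet the DLT definition. Those are the ones section 8.12 does not replace.

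Nor do the documents establish that 24-month data on reactors are lost. Section 8.12 asks those who wish to withdraw after dosing to continue the safety visits or allow access to routine data, and section 7.10 keeps data already collected. That offer is worded for voluntary withdrawal, so for an enforced one the visits are not guaranteed.

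Replacement is optional. The DMC reviews every withdrawn patient, sees safety data after the first and last patient of each cohort (section 10.3), and would see a stopped infusion. Replacing a child who cannot be evaluated at the assigned dose is also defensible in itself, and simply counting a partly dosed child as free of DLT would make escalation easier.

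These points narrow the concern and shape the fix. They do not supply a rule for toxicity-driven withdrawal or for 'not determined'.

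**Conclusion.** The point holds in a limited form. Followed as written, sections 7.10 and 8.12 together allow a child who reacts below the DLT threshold to lose the guaranteed Day 14 and Day 28 assessment and be replaced, with no exception for withdrawal caused by the product.

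The size cannot be derived from the protocol. In the middle scenario, P(0/3) is 64% with all counted against 73% with replacement, and the high dose is declared tolerated in 67% against 81%. Among the tabled scenarios with h above d, the gap in the latter runs from about 2 points (78.2% against 80.6%) to about 55 (26.0% against 80.6%). A downward bias requires reactors to have the higher week-4 DLT risk. That is plausible for children removed because they reacted, but it is an assumption. Whatever the true rates, the escalation rule should not depend on an undefined term and a discretionary replacement.

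**What to change.** **Section 7.10.** Separate stopping the infusion from leaving the study. Every child who received any TR006 stays in the scheduled safety visits, at least to Day 28 for DLT assessment and to Month 24 unless consent is withdrawn. Reconcile this with section 4.2.1. When an infusion is stopped remains a matter for the clinical team.

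**Section 8.12.**
- Allow replacement without further condition only when withdrawal is unrelated to toxicity.
- A child whose infusion was stopped, or who left, because of a TR006-related event stays in the DLT count and is not automatically replaced. The DMC records a DLT ruling before the cohort decision.
- A partly dosed child ruled 'no DLT' or 'not determined' does not count as a tolerated case towards escalation at the assigned dose, and is reported in all safety analyses.

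**Effect.** If each such child ruled 'no DLT' leads to one further child, the DLT rate per counted child is [(1 − r)d + rh] / [1 − r(1 − h)]. For r = 10%, d = 10%, h = 50% this is 0.14/0.95 = 14.7%, and P(0/3) is 62.0%. With h = 0 it is 0.09/0.90 = 10%, as under replacement, so the fix does not make escalation easier than the present rule. It is slightly cautious when the risks are equal: with h = 10%, 0.10/0.91 = 11.0%, and P(0/3) is 70.5% against 72.9%.

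**Cost.** A few protocol sentences, matching consent wording and no new visits. Occasionally one more child is needed to complete a cohort. If every reactor needed one, the expected number infused for 9 evaluable would be 9/(1 − r): 9.5, 10.0 and 11.3 at r = 5%, 10% and 20%. The present replacement rule already permits the same extra recruitment.

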7.11 Definition of End of Trial

The end of trial will be defined as the database being locked following all participants having completed their final follow-up visit, the data from all visits entered on the database and all queries resolved.

All SAEs will be followed up for a further 30 days after the last participant's final follow-up visit date or until resolution.

8 Treatment Regimens

The thymus (used to make TR006) will be collected from study participants at GOSH on the Day of Transplant (surgery) study visit. The Investigator (or the person to whom the Investigator has delegated this responsibility to) will attend the cardiac surgery and collect the thymus tissue explanted by the surgical team using aseptic technique. The thymus tissue will be put into a sterile pot containing MACS tissue storage solution. As the surgery may occur unpredictably out of hours, the tissue may need to be stored in a temperature-controlled fridge (at 2-8°C) prior to the CRF GMP Unit at Guy's and St Thomas' NHS Foundation Trust for processing. The thymus starting material may be need to be stored at GOSH for up to 48 hours prior to transfer to the CRF GMP Unit. Transport of the starting material will be carried out at 2 - 8°C in a validated transport box with a data logger that monitors the storage temperature.

Once the thymus is ready to be processed, initially, the thymus is mechanically digested to obtain a cell suspension of thymocytes. CD3+CD4+CD8-CD25+ T cells are isolated by depleting CD8+ cells using immunomagnetic beads (CD8 microbeads, Miltenyi Biotec) followed by CD25 enrichment (CD25 microbeads, Miltenyi Biotec). Isolated Tregs are expanded polyclonally using α CD3/ α CD28 microbeads (1:1 bead:cell ratio, CTS Dynabeads Treg Xpander, ThermoFisher Scientific) for up to 23 (+/- 1) days in the presence of rapamycin (100nM) and IL-2 (1000 IU/mI).

The resulting product lacks of CD8 positive cells and is highly enriched in CD4+CD25+CD127-FOXP3+ cells. In addition, the product expresses a high level of CTLA4, CD62L, CXCR4 and Helios while homing receptors like CCR6, CCR7, CXCR3 and functional markers like CD39 are poorly expressed.

TR006 will be packed in a 10mL CryoMACS Freezing Bag (CE-Marked medical device).

8.1 Dosage schedules

Eligible patients will receive a single dose of TR006 at 1-3 x 10⁶ TR006/Kg or at 5-10 x 10⁶ TR006/Kg.

Patients will be dosed at Great Ormond Street Hospital.

8.2 Route of Administration

The TR006 IMP will be thawed by the study team at GOSH, and the thawed 10 mL (1-3 x 10^6 TR006/Kg or at 5-10 x 10^6 TR006/Kg) IMP bag will be spiked to a giving set for infusion. The procedure will be detailed in the TR006 Handling Instructions.

After the TR006 has been administered to a participant, up to 10mL of saline solution (equivalent to the volume of TR006 dose) will also be used to flush the dose to make sure that all the cells are given to the patient.

The infusion will be administered intravenously by a suitably trained and delegated member of the study team.

8.3 Maximum dosage allowed

 $5-10 \times 10^{6}$ TR006/Kg is the highest dose being evaluated in this trial.

8.4 Maximum duration of treatment of a subject

The participants will only receive the treatment once at Baseline (3-6 months post-surgery).

The infusion should take around 30 minutes to complete for a single dose.

8.5 Dosage modifications

If the required dose cannot be manufactured the patient may have to be dosed at a lower dose than the dose originally planned. In such a situation, the Data Monitoring Committee and Statisticians should be informed.

8.6 Drug production

Please refer to IMPD for the full product specification and manufacturing process.

TR006 will be manufactured at: CRF GMP Unit [name]

Site licence number: 11387. Site ID number: 6280106

The starting material, thymocytes, will be obtained from discarded thymus for each patient during surgery or during the time of having a pump assisted device fitted in (this can be up to 1 year presurgery). In order to isolate bulk Tregs, thymocytes will be depleted from the CD8+ cells and the remaining fraction will be enriched for CD25. After isolation, enriched Tregs will be activated with α CD3/ α CD28 microbeads (1:1 beads to cell ratio) and cultured in the presence of IL-2 (1000IU/mL) and rapamycin (100nM).

The manufacturing process will take between 10-23 (+/- 1) days and cells will go through (up to) three rounds of stimulations (Day 0, Day 10+/-1 and Day 17+/-1). Once the cells have been harvested, activation beads will be removed and the final product will be formulated to the correct cell concentration for the patient dose in CryoStor CS10 Cell Freezing Medium and frozen in a cryoprotective freezing bag.

8.7 Drug storage

Once manufacture is completed, TR006 will be transferred to a controlled rate freezer, before transfer to the vapour phase of a liquid nitrogen storage tank (-150°C), where it will be stored prior to administration to the patient. The bag will be labelled with appropriate labels for the defined storage conditions.

Once the patient is ready to receive the TR006 IMP, it will be shipped in a liquid nitrogen vapour phase dry shipper to GOSH and then thawed by the study team at GOSH immediately prior to administration.

8.8 Known drug reactions

As TR006 has never been extensively tested in humans before, there is currently no available list of medical events/reactions that are expected for the ATIMP. Hence any serious adverse events that are deemed related to the ATIMP (SARs) will be considered SUSARs.

8.9 Concomitant Medications

Data will be collected relating to concomitant medications at every visit. Concomitant medication covers all medications and significant non-drug interventions. A complete history of medication taken by the participant will be recorded in the relevant Concomitant Medication Log/electronic Case Report Form at screening.

All concomitant medications (including over-the-counter or prescription medicines, vitamins and/or herbal supplements) and the doses taken by a patient during their participation in the trial must be recorded in the relevant section of the Concomitant Medication Log/electronic Case Report Form.

Participants in this trial will receive the local standard treatment for those undergoing a heart transplant. This encompasses pre-surgery medication, general anaesthesia, recovery from anaesthesia, pain control medication, and anti-infective therapy (viral, fungal and bacterial).

Immunosuppression therapy should be given as per local standard protocol. Typically after transplant, the below immunosuppressive medications (in Table 9) are prescribed and will usually be routinely taken by all patients. Depending on each patient's clinical course and treatment plan, there may be variations of the dosing schedule and/or drug choice.

Drug	Regime	Dose
Basiliximab	 First dose within two hours prior to organ implantation. Second dose on day 4 post-transplant. 	 <35kg: 10mg iv slow bolus over 3-5 minutes. >35 kg: 20 mg iv slow bolus over 3-5 minutes.
Corticosteroids	 IV methylprednisolone - 15 minutes prior to cross clamp release (peri- operative). IV methylprednisolone given in intensive care post-operatively during recovery for first few days until orally taking medication when switched to oral prednisolone. 	 Peri-operative dose 15mg/kg iv in theatre. In intensive care post op: Day 1: 10mg/kg iv daily in the morning. Day 2: 2mg/kg iv daily in the morning. Day 3: 2mg/kg iv daily in the morning. Day 4: 1 mg/kg iv daily in the morning and continue until switched to oral medication.
		 When able to take oral medicines (and tacrolimus is in range) convert to oral prednisolone (1:1 on mg basis): once

Table 9: Routine Post-Transplant Immunosuppression Therapy:

		daily in the morning.
		 If no signs of rejection: aim to wean to 0.1 to 0.15mg/kg daily by discharge or 4 weeks. Wean off before 3 month biopsy date if no previous rejection.
Tacrolimus	Tacrolimus orally / nasogastric post	Tacrolimus continued orally post-operation
	operatively.	(lifelong) as per blood levels (depending on
		time scale reached post- transplant):
	Usual start dose: U.USmg/kg (max 2mg	• 0-6 months: 10 - 14ng/mL
	fillially) of ally twice a day.	= 0-12 monutes: 8 - 12ng/mL
	Take trough lovel in the morning before	
	socond or third doso. Target range is 10.15	
	ng/mL immediately nost-operation	
Myconhenolate	Myconhenolate mofetil: iv 600mg/m2 twice	When tolerating oral medications patients
Mofetil (MMF)	a day. First dose immediately post-	will continue oral dosing for 600mg/m^2
	operation.	(rounded up to the nearest whole tablet).
		This is remains a long term
		immunosuppressant medication unless
		clinical indication to reduce or stop as per
		Transplant team advice).
		 For children < 2 years old
		mycophenolate mofetil reduced to
		300mg/m ² orally twice a day when
		tacrolimus stable in range.

Alternative immunosuppressants (such as Sirolimus, Ciclosporin, Azathioprine and Anti-thymocyte globulin (Thymoglobuline[®]) infusion) may be considered in specialised treatment schedules to prevent organ rejection. This may be done at the discretion of the local Transplant Team in specific clinical scenarios. These are not first line treatments, therefore, the required dosing schedules have not been extensively detailed here and local SOPs will be consulted if these are deemed necessary.

As per the standard of care oral medications for post-heart transplant patients at GOSH, additional medications may be recommended to manage traditional cardiac risk factors and to also reduce the risk of opportunistic infections. This is summarised below (in **Table 10**) and, where required, will be maintained for the study participants:

Indication	Drug and dose
Hypertension	Options of agents as below. Usually one agent is commenced to maintain blood pressure target range for age.
	• Amlodipine 0.1 - 0.2mg/kg (max 0.4mg/kg or 10mg) orally daily.
	 If no renal impairment and persistent high blood pressure: Captopril initially 0.1mg/kg orally tds increasing to 1mg/kg tds as tolerated (and adult hypertension dose 12.5 - 25mg tds)
	For older children:Enalapril initially 0.05 mg/kg bd.
Dyslipidaemia and CAV	No pravastatin under 1 year.

Table 10: Routine Post-Transplant Therapy:

	Pravastatin (if above 1 year old):
	■ 1-2 years: 2.5 to 5mg orally at night
	$\blacksquare 2 - 12$ years: 5 to 20mg orally at night
	If years: 20 to 20mg orally at hight
Cardiac Allograft	Aspirin: 5mg/kg (max 75mg) orally daily with food
Vasculonathy	
Prophylaxis of	Co-trimovazole: all doses are given orally twice daily on Mondays
Pneumocystis carinii	Wednesdays and Eridays (life-long):
Theumocysus carini	$\mathbf{I} < 4ka; 20mg/kg/day in 1 or 2 docos$
	= 4 Ekg. Comp hd
	= 4 -5kg; outrig bu
	• 0 -10kg: 120mg bd
	■ >40kg: 480 mg ba
Pronhylavis of	For the prophylaxis of Toxonlasmosis gondii in donor positive / recipient
	nogative transplants, so trimevazele is given at the same above dose twice a
	dev event dev for 6 menths
Dranky Javia of Llarnas	
Simpley views	
Simplex virus	■ 1 month - 2 years: 100mg 8-hourly.
	■ 2 years - 18 years: 200mg 8-hourly.
	Aciciovir is started when renal function is adequate and able to tolerate oral
	medication. Prophylactic doses are given for 3 months.
	If infantion accurs change to introveneus acidewir E00mg/m2 tds
Currente mentie en (high wing)	
symptomatic or (nigh viral	
titre CIVIV) Infection	
	Ganciclovir: IV 5mg/kg 12 hourly for 7-14 days then maintenance 5mg/kg
	once daily.
	Valganciclovir: Dosing as per product literature and local protocols, guided
	by drug monitoring.

Anaesthesia related medication will not be regarded as concomitant medication.

Prohibited medications:

Other experimental drug therapies will not be allowed for the duration of the trial.

Of note, there are medications and vaccinations that are contraindicated for transplant patients because of interactions with tacrolimus immunosuppression (detailed in the British National Formulary for Children). [40]

